Most outcomes will be assessed during a single home visit; however; some assessments will occur across the 18 mo. active intervention (Table 2). Weight, height and waist circumference will be obtained between 7-10 a.m. following a minimum 12-hr. fast. Assessments will be completed by trained staff blinded to condition. Our experience with similar trials suggests the proposed assessments will require ~30 min. Staff will receive refresher training and complete reliability assessments for physical measures 2-3 times/yr.

Note: WC = waist circumference

(age, race/ethnicity, sex, current PA level) for both participants and their study partners will be collected at baseline.

Anthropometrics (Weight, height, BMI%ile, waist circumference) Participants will be weighed in shorts and a t-shirt between 7 and 10 AM, in duplicate, on a calibrated scale (Model #PS6600, Belfour, Saukville, WI) to the nearest 0.1 kg. Standing height will be measured in duplicate with a portable stadiometer (Model #IP0955, Invicta Plastics Limited, Leicester, UK). BMI%ile will be calculated using the CDC BMI%ile calculator for children and teens (<http://apps.nccd.cdc.gov>). Waist circumference will be assessed using the procedures described by Lohman et al. Three measurements will be obtained with the outcome recorded as the average of the closest 2 measures.

Quality of life. QOL will be assessed with the Personal Well-Being Index-Intellectual Disability.

Energy and macronutrient intake. Diet intake will be assessed during 3 consecutive days (2 wk days and 1 wk end day) starting the weekend prior to the outcome assessment date using standard proxy assisted 3-day food records augmented with food photos. IDD. Participants with assistance from a caregiver (if necessary) will be asked to take before and after photos of all food and beverages consumed at home over 3 days with the iPad camera. Participants will complete hard-copy proxy-assisted (parent) diet records to account for details about food and beverage not available from photos such as skim or whole milk, etc. To facilitate accurate recording, instructions developed by [name] ("How to record your food record") that describes the food record and provides detailed examples to assist with the estimation of portion size, as well as instructions on how to take food photos, will be loaded into the iPad. Calendar prompts will be programmed into the iPad to remind all participants to comply with the photo/record protocol. The iPad automatically date and time stamps all photos for easy identification. During the outcome visit the 3-day food record and photos will be reviewed to clarify food record entries. The energy and macronutrients of the diet record information will be assessed using Nutrition Data System for Research (NDSR version 2016, University of Minnesota, Minneapolis, MN).

Medication Record. At each assessment period of baseline and months 6, 12, 18 all medications the participant is currently taking will be documented. The information gathered will include the medication name, reason for taking, amount and frequency of dosage as well as the cost of the medication. This information will be collected to monitor any cost changes in medication throughout the study and will be included in the cost analysis. .

PA. Compliance with PA recommendations will be assessed using an accelerometer (min. of MVPA) over 7 consecutive days at baseline, 6, 12 and 18 mos. Participants will be asked to wear the accelerometer belt on their non-dominate hip. A minimum of four 10-hr. days at each time point will be considered a valid observation (85).

Attendance: The health coach will record attendance at all health education sessions. The participant will only be considered present if they complete session.

Semi-structured interview: [name] will conduct structured interviews by phone with a 20% random sample of participants and study partners from both intervention groups following completion of the intervention to gather information which might be useful in improving the intervention and/or implementing the intervention in settings serving adults with IDD. Topics will include, preference for FTF or RD, intervention length, difficulties in complying with intervention components, suggestions for improving the intervention, overall satisfaction, including the diet and PA recommendations, behavior sessions, and satisfaction with health educators. All interviews will be recorded and transcribed verbatim. Data will be entered into a qualitative data software program (Atlas.ti 7, Berlin, Germany). Any coding disagreements will be brought to the research team for review and discussion until 100% agreement is reached. A content analysis of the transcribed interviews will be conducted using the method suggested by Miles and colleague (91) and further described by Ryan and Bernard (92) to explore trends and identify common themes across interviews using an inductive method.

Study Partner Questionnaire. Study partner self-efficacy for providing assistance with weight management will be assessed using the 6-item scale developed by Heller et al. (89). Each statement is rated from 1 (strongly disagree) to 5 (strongly agree). Cronbach's alpha = 0.77.

Cost Analysis. Our previous trial comparing FTF and RD (group phone) for weight management (38) suggests higher costs in the FTF group due to costs for both travel and time associated with home visits. We will conduct a cost effectiveness analysis using between group differences in mean weight loss at 6 and 18 mos. (76). The cost perspective for all analyses will be societal. We will collect data on both program (health educator time, supplies, iPads) and participant/study partner costs (time), prospectively. Time is a component of intervention cost, as time devoted to an intervention cannot be used for work or leisure (77). Participant and study partner time will be valued at the local median hourly wage. These costs, which may be half of the total costs (78, 79), will be gathered via survey (80). We will conduct sensitivity analyses that vary the value of participant/study partner time from \$0.00 to the median hourly wage. The gold standard for measuring cost is a time study, based on a validated flowchart (81, 82). We will validate flowcharts for both study arms and use time studies to measure health educator time and program records to measure cost of supplies. Weight management programs have effects in addition to weight loss (e.g., increased vitality or enhanced attractiveness), thus the value of a program to clients may be imperfectly measured by objective outcomes (weight). Contingent valuation, in which participant's express preferences for programs, will be used to examine the perceived worth of the RD and FTF formats at 6 and 18 mos. (83). If the preference questions have acceptable psychometric properties conditional logistic regressions, with adjustments for clustering by health educator, will be used to analyze how differences in client attributes, anticipated costs/gains affect preferences for delivery formats.

COVID 19: During the Covid-19 pandemic restrictions all assessment materials will be delivered to participant homes. All materials will be disinfected beforehand and will be delivered to participant's homes. A stamped, self-addressed envelope will be included to allow participants to mail surveys and accelerometers back. All face-to-face meetings will be conducted by phone.

Statistical Methods

Analysis plan. Primary aim. We will construct a two-sided 95% confidence interval for the difference in mean 6 mo. weight loss between the RD and FTF groups. If the lower limit of the confidence interval is >-3 and the upper limit is > 0 we can conclude that RD is non-inferior to FTF. If we find that 6 mo.

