Remote Delivery of Weight Management for Adults with IDD

NCT03291509

MPIs: [name] and [name]

Protocol and Analysis Plan

Last updated 3/20/2020

Aims and Hypothesis

Adults with intellectual and developmental disabilities (IDD) represent an underserved segment of the US population with a high prevalence of obesity, obesity related chronic disease, and limited options for weight management. Multicomponent weight management, which involves on-site group behavioral counseling, reduced energy intake, and increased physical activity (PA) is problematic for adults with IDD. On-site group sessions may be inappropriate for adults with IDD who have diverse cognitive, communication and social skills, and depend on caregivers for transportation to meeting sites/exercise facilities, and assistance with meal planning, food shopping and meal preparation. Our group, and others, have demonstrated that adults with IDD living with a parent, or in supported living, can achieve clinically meaningful weight loss (3-5%) in response to multicomponent home-based interventions, i.e., face-to-face (FTF). For example, we have evaluated the effectiveness of an enhanced Stop Light Diet (eSLD) as part of a FTF weight management intervention in adults with IDD in 2 previous trials. The eSLD simplifies meal planning, food shopping and meal preparation making it potentially useful for adults with IDD and their caregivers. The eSLD included 2 ~ 200 kcal portion-controlled entrées/d, 2 ~100 kcal shakes/d, 5 one-cup servings of fruits/vegetables/d, and ad-libitum non-caloric beverages. Additional low energy foods were selected using the SLD system: green (low energy), yellow (moderate energy), and red (high energy). Our single arm pilot trial in adults with IDD (n=66) found the eSLD, plus monthly at-home FTF behavioral sessions (adult + caregiver), plus increased PA, achieved weight loss of -6.4% and -8.7% at 6 and 12 mos., respectively. Based on this data we conducted an adequately powered 18 mo. trial (6 mos. weight loss/12 mos. maintenance) (DK83539) in adults with IDD who were randomized to an eSLD (n=77) or a conventional diet (CD, n=72). Both groups completed monthly at-home FTF behavioral sessions (participants & caregiver) and received recommendations for increased PA. Six-month weight loss was significantly greater in the eSLD (-7.0%) compared with the CD group (-3.8%, $p<0.001$); however, both groups had similar weight loss at 18-mos. (eSLD = -6.7%, CD = -6.4%, $p=0.82$). The FTF intervention produced significant weight loss; however, the time and cost associated with FTF delivery (travel + sessions) limits the potential for scaling and dissemination. This suggests the need for the evaluation of alternative strategies, such as remote delivery using video conferencing, which may produce significant weight loss at lower cost with improved potential to reach greater numbers of this underserved group. Therefore, we propose a 24 mo. randomized trial (6 mos. weight loss, 12 mos. maintenance, 6 mos. no-contact follow-up) to compare 2 weight management interventions delivered to adults with IDD in their home, either remotely (RD) via video conferencing (Zoom software) on a tablet computer (iPad mini), or during FTF home visits. Both intervention arms will include monthly at-home behavioral sessions (adult + caregiver), an eSLD, and increased PA. The RD arm will include group PA delivered using video conferencing (2 session/wk.) and will use commercially available web-based applications for self-monitoring/participant feedback for diet (Lose it!), PA (Fitbit activity tracker), and weight (Wi-Fi scales). The FTF arm will be identical to the intervention shown to be effective in our previous trial (DK83539) and will include self-directed PA, self-monitoring of diet and PA using paper/pencil logs, and weight assessed during monthly home visits. We will address the following aims:

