
Primary aim: To determine if weight loss (0-6 mos.) in the RD group is non-inferior to FTF group. Non-inferiority will be declared if mean weight loss for RD is no worse than FTF, within statistical variability, by a margin of -3 kg which represents the maximal between group difference that would yield clinically meaningful weight loss in the RD group

Secondary aims: We will compare changes between the RD and FTF groups in the following variables across 24 mos.: 1) Mean weight loss; 2) The proportion of participants who achieve clinically meaningful weight loss ($\geq 5\%$); and 3) Quality of life. We expect similar changes in the RD and FTF groups for each of these secondary aims. We will also conduct cost, cost-effectiveness and contingent

valuation analyses to compare the RD and FTF groups. We expect reduced costs in the RD compared with the FTF group.

Exploratory aim: We will examine the influence of the following process variables/participant characteristics to identify salient factors impacting weight loss across 18 mos.: behavioral and PA session attendance, compliance with recommendations for diet (energy intake, number of entrées/shakes, servings of fruits/vegetables, PA (min of moderate-vigorous PA), self-monitoring of diet and PA, sex, age, IDD diagnosis, caregiver self-efficacy/turnover, and obesogenic medications.

Background and Significance

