
useful for adults with IDD and their caregivers. First, we evaluated the effectiveness of the eSLD for weight loss (6 mos.) and maintenance (6 mos.) in combination with monthly, at-home, face-to-face (FTF) behavioral sessions with participants and a caregiver, and increased PA, in a sample of 66 overweight/obese adults with IDD (25). Mean weight loss was -6.4% and -8.7% at 6 and 12 mos., respectively. We recently completed an 18 mo. trial to compare the effectiveness of the eSLD with a conventional meal plan diet (CD) as part of a multicomponent intervention for both weight loss (0-6 mos.) and maintenance (7-18 mos.) in adults with IDD (DK83539). Overweight/obese adults ($BMI \geq 25 \text{ kg/m}^2$) with mild to moderate IDD, living either in the community with parents/guardians, or in supported living with a paid caregiver, who served as a "study partner", were randomized to either an eSLD (n=77) or CD (n=72). In addition to an energy reduced diet, participants were asked to increase PA (150 min./wk.), self-monitor diet and PA, and attend behavioral counseling/educational sessions conducted by a health educator during monthly home visits. The sample was 57% female, 17% Down Syndrome, with a mean age and BMI of 36.5 yrs. and 36.9 kg/m², respectively. The majority of participants (~74%) lived in a group situation with support from paid staff. Weight loss (6 mos.) was significantly greater in the eSLD (-7.0%) compared with the CD group (-3.8%, $p<0.001$). The proportion of participants achieving weight loss of $\geq 5\%$ at 6 mos. was significantly greater in the eSLD (62.7%,) compared with the CD group (40.3%, $p=0.013$). However, at 18 mos. mean weight loss between groups did not differ significantly (eSLD = -6.7%; CD = 6.4% $p=0.82$). Among participants completing the 18 mo. intervention 57.4%, and 48.9% achieved $\geq 5\%$ weight loss from 0 to 18 mos. in the eSLD and CD groups, respectively. Weight change across 18 mos. did not differ by the type (family vs. paid staff) or number of study partners, the number of participants living in a residence, the use of obesogenic medications, or between adults with or without Down Syndrome. These results suggest the robustness of this approach in adults with IDD. In sum, the results from our 12 and 18 mo. trials were encouraging; however, the logistical burdens and costs associated with delivering a weight management intervention to individuals in their home greatly limits the potential for scaling and implementation of this approach by community and other agencies serving adults with IDD. Thus, alternative strategies for delivering weight management to adults with IDD are needed.

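### The plan does not show that -3 kg is the largest deficit that keeps remote-delivery loss clinically meaningful, and its decision rule never checks that arm's own loss

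*Combined protocol and SAP*

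**What the plan says.** Aims and Hypothesis, Primary aim: RD is to be judged non-inferior if its mean loss falls short of FTF's by no more than 3 kg. The plan says this margin "represents the maximal between group difference that would yield clinically meaningful weight loss in the RD group". No threshold, expected FTF loss or baseline weight is given to support this.

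Statistical Methods, Analysis plan: "We will construct a two-sided 95% confidence interval for the difference in mean 6 mo. weight loss between the RD and FTF groups". The rule has two parts: "If the lower limit of the confidence interval is >-3 and the upper limit is > 0 we can conclude that RD is non-inferior to" the face-to-face arm. Neither part refers to the loss in RD itself.

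Clinically meaningful loss is described in two ways:

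- The opening of Aims and Hypothesis says adults with IDD "can achieve clinically meaningful weight loss (3-5", in percent of body weight.
- Secondary aim 2 is "The proportion of participants who achieve clinically meaningful weight loss", with at least 5% in brackets. Background, under weight management in adults with IDD, also attaches at least 5% to the term.

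On expected FTF loss, the Aims state that the FTF arm repeats the intervention of the earlier randomized trial. Background reports of that trial: "Weight loss (6 mos.) was significantly greater in the eSLD (-7.0%) compared with the CD group". The single-arm pilot lost 6.4% at 6 months.

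**The concern.** The margin comes with a stated property: a deficit of up to 3 kg leaves RD with clinically meaningful loss, and no larger deficit would. A reader will therefore take a non-inferiority result to mean that RD produces meaningful loss. That inference needs three things the plan does not give: a single threshold, the FTF loss assumed, and the baseline weight that turns kilograms into percent. Without them the property cannot be checked, and under one of the plan's two definitions it does not hold. It also depends on FTF performing as it did before, which the decision rule does not verify.

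**Working it through.** The plan shows no calculation behind 3 kg, so there is no figure to reproduce. The check converts the margin to percent.

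**Inputs from the documents.** Margin 3 kg (Primary aim). FTF 6-month loss F = 7.0% (randomized trial) or 6.4% (pilot). Thresholds t = 3% and 5%. Mean BMI 36.9 in the earlier trial (Background). Entry cap 400 lb = 181.4 kg (Participant eligibility).

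**Assumption.** Mean baseline weight W is not given. BMI 36.9 × height² gives 88.7 kg at 1.55 m, 100.5 kg at 1.65 m and 119.6 kg at 1.80 m. I use 90-120 kg.

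**1. RD loss if the true deficit is exactly 3 kg:** F − 300/W.

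| W (kg) | 3 kg as % | RD, F = 7.0% | RD, F = 6.4% |
|---|---|---|---|
| 90 | 3.33 | 3.67% | 3.07% |
| 100 | 3.00 | 4.00% | 3.40% |
| 110 | 2.73 | 4.27% | 3.67% |
| 120 | 2.50 | 4.50% | 3.90% |

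The range is about 3.1-4.5%. At 83.0 kg (height 1.50 m) with F = 6.4% it would be 6.4 − 3.61 = 2.8%.

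**2. Mean weight at which 3 kg is exactly the maximal deficit:** W = 300/(F − t).

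- t = 5%: 300/2.0 = 150 kg, or 300/1.4 = 214 kg. The first needs a height of 2.02 m at BMI 36.9. The second exceeds the entry cap.
- t = 3%: 300/4.0 = 75 kg, or 300/3.4 = 88.2 kg.

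**3. Largest deficit that keeps RD at t:** (F − t) × W/100.

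- t = 5%: 2.0 kg (F = 7.0%) or 1.4 kg (F = 6.4%) at 100 kg; 1.3-2.4 kg over 90-120 kg.
- t = 3%: 4.0 kg or 3.4 kg at 100 kg; 3.1-4.8 kg over 90-120 kg.

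Over this weight range, 3 kg is too wide to keep 5% and narrower than the maximum that keeps 3%.

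**4. What the full rule allows to be observed.** Let the interval be d ± h. The conditions d − h > −3 and d + h > 0 add to 2d > −3, so d > −1.5 kg. At 100 kg the observed RD loss at declaration then exceeds 7.0 − 1.5 = 5.5%, or 6.4 − 1.5 = 4.9%, provided FTF performs as before.

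**5. If FTF underperforms.** The rule limits only the difference. At 100 kg, if FTF loses 5%, an observed deficit just under 1.5 kg can pass with RD near 5 − 1.5 = 3.5%. If FTF loses less than 4.5%, RD can pass below 4.5 − 1.5 = 3.0%, which misses both definitions.

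**6. How often a deficit that breaks the 5% reading would pass.** The documents give no standard error (SE), so I assume 0.765-1.5 kg. RD passes if d exceeds the larger of −3 + 1.96·SE and −1.96·SE.

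- True deficit 2.0 kg: P(Z > 0.5/0.765) = 26% and P(Z > 1.94/1.5) = 10%.
- True deficit 1.4 kg: P(Z > −0.1/0.765) = 55% and P(Z > 1.34/1.5) = 19%.

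Smaller SEs lower these figures, because the upper-limit condition then governs.

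**The case against.** The strongest reply is that the Aims section itself supplies a definition the margin meets. The 3.1-4.5% range lies inside 3-5% at every weight from 90 to 120 kg, and Background calls loss under 3% minimal. One combination even makes 3 kg exactly maximal: a 4% threshold, F = 7.0% and 100 kg, since (7.0 − 4) × 100/100 = 3.0 kg. This stands. A reader might infer that the margin simply fails its purpose, and the documents do not support that. They show two definitions and no statement of which one the margin uses.

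Second, the 5% figure in Secondary aim 2 is a cut-off for individual participants, whereas the margin concerns group means. This stands in part. Background, however, uses the 5% figure for what whole trials achieved, and the summary of significance calls a mean loss of 7% clinically meaningful.

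Third, a reader might infer that RD losing 3-4% is a likely declared result. It is not. A true deficit of exactly 3 kg passes at most about 2.5% of the time, and step 4 bounds what can be observed.

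Fourth, it is tempting to say that RD at the margin would do no better than the earlier trial's conventional diet, which lost 3.8%. Three kg equals that 3.2-point gap only near 3/0.032 = 94 kg. The two diets were similar at 18 months (6.7% and 6.4%), and both arms here use the enhanced diet. The comparison should not be made. Nor should the margin be applied to one light participant near the BMI entry limit, because it is a margin on means.

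**Conclusion.** The concern holds in limited form. The claim about what -3 kg preserves is not supported by anything the plan shows. Against at least 5% it is wrong at any plausible mean weight: it needs 150 kg with FTF at 7.0%, or 214 kg with FTF at 6.4%. Against 3%, RD at the margin is acceptable from 75 kg or 88 kg upward, but 3 kg is then the maximum only at those weights. The conclusion on 5% does not depend on the assumed 90-120 kg. The 3.1-4.5% range does, and it also assumes FTF repeats 6.4-7.0%.

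Separately, the rule contains no check on RD's own loss, so non-inferiority alone cannot establish that RD's loss is clinically meaningful. The margin itself need not change. What must change is the property attributed to it and the conclusion drawn from it.

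**What to change.** 1. Keep -3 kg as the formal margin.
2. Choose one definition of clinically meaningful loss, say whether it applies to a group mean or to individuals, and use it throughout.
3. Correct or delete the sentence on what the margin preserves. If it stays, give the threshold, FTF loss and baseline weight behind it.
4. Report mean percent weight change at 6 months with 95% confidence intervals for each arm and for the difference. This is supportive and carries no second formal margin. A 2-point margin (7.0% minus 5%) would build in the disputed 5% reading.
5. Claim clinically meaningful loss in RD only if the lower 95% limit of RD's own mean percent loss reaches the chosen definition. Otherwise report only that RD was within 3 kg of FTF.

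The cost is a change of wording and one extra table, with no added participants. The downside is that the permitted claim may be less favourable. Items 2 and 5 should be settled before outcome data are compared by arm.
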